##### 1.2 START DATE

##### FINISH DATE

Start August 2022, end December 2023

# *Old Civil Hospital of Guadalajara*

## "FRAY ANTONIO MAYOR"

Teaching Subdirectoriate  
Research Coordination

### 2.1 PROJECT SUMMARY

The purpose of this clinical trial is to carry out research on the effect on hemoglobin and renal function of the intravenous administration of iron dextran as a repletion strategy in patients with iron deficiency anemia and acute kidney injury, in which the patient You may benefit from this medication since it is expected to correct anemia, iron deficiency and renal function parameters, when compared with a control group (placebo), the safety of the drug will also be evaluated by recording adverse effects. I will point out with the patient the risks and benefits of including her in this type of study and I will answer all the doubts that arise, and I will also immediately report any serious adverse effect to the research ethics committee.

Version 2.0, 29 June 2023

Effect of intravenous iron repletion on renal function in patients with iron deficiency and acute kidney injury, clinical trial. June 2023, HCG/CEI-1232/22

[name] [contact], [name] GUADALAJARA, JAL

# *Old Civil Hospital of Guadalajara*

## "FRAY ANTONIO MAYOR"

Teaching Subdirectorato  
Research Coordination

### 2.2 INTRODUCTION

Acute kidney damage is a complication that occurs in up to 30% of hospitalized patients. Iron deficiency has a high incidence in the population of critically ill patients and has been associated with multiple complications such as the development of anemia and renal dysfunction. The presence of iron deficiency, anemia and acute kidney injury is a common combination in critically ill patients and iron deficiency has been shown to promote mitochondrial dysfunction and this can be improved with intravenous iron correction, as has happened in clinical trials of patients with failure exacerbated cardiac arrest, improving its clinical evolution.

The kidney is the second organ with the most mitochondria and mitochondrial dysfunction is a new therapeutic goal in acute kidney injury. It is possible that this combination is associated with an unfavorable clinical course in these patients.

### 2.3 JUSTIFICATION

There is insufficient evidence for the implementation of intravenous iron in order to improve the parameters of iron deficiency anemia in patients with acute kidney injury.

To our knowledge, there is no clinical trial that has explored our objectives.

Version 2.0, 29 June 2023

Effect of intravenous iron repletion on renal function in patients with iron deficiency and acute kidney injury, clinical trial. June 2023, HCG/CEI-1232/22

[name] [contact], [name] GUADALAJARA, JAL

# Old Civil Hospital of Guadalajara "FRAY ANTONIO MAYOR"

Teaching Subdirectorato  
Research Coordination

## 2.4 SCIENTIFIC BACKGROUND

Acute kidney injury (AKI) is a serious complication that is independently associated with poor outcomes [1, 2]. Approximately one in five patients with non-severe sepsis develops AKI [3], which increases to two-thirds in critically ill patients. About 50% of ICU patients with AKI die (4-12), and those who survive an episode of AKI have a higher risk of progressing to chronic kidney disease (CKD). Currently, there are few pharmacological therapeutic options available to prevent or treat AKI, and management is limited to alleviating hemodynamic and toxic renal lesions. support measures, such as dialysis.

Iron deficiency occurs in up to 30% of hospitalized patients and has been linked to worse clinical evolution, even in the absence of anemia. This iron deficiency is worse even when anemia figures are reached. It has been documented that critically ill patients develop anemia as part of the process of their pathology. It has been seen that during processes of exacerbation of pathologies such as heart failure, the administration of intravenous iron avoids the probability of hospitalization and clinical evolution (13-16). It has been shown that in DRA there is mitochondrial dysfunction (17), specifically in the renal tubule where the greatest amount of mitochondria is concentrated,

Version 2.0, 29 June 2023

Effect of intravenous iron repletion on renal function in patients with iron deficiency and acute kidney injury, clinical trial. June 2023, HCG/CEI-1232/22

# Old Civil Hospital of Guadalajara

## "FRAY ANTONIO MAYOR"

Teaching Subdirectorato  
Research Coordination

### 2.5 OBJECTIVES

#### **Primary objective:**

The endpoint of interest was the proportion of patients meeting one or more criteria for Major Adverse Kidney Events within 30 days (MAKE30): in-hospital mortality; receipt of new RRT; or persistent renal dysfunction.

In hospital mortality was defined as death from any cause prior to hospital discharge censored at 30 days after ICU admission. Receipt of new RRT was defined as receipt of any modality of RRT between ICU admission and the first of (1) hospital discharge or (2) 30 days in a patient not known to have received RRT prior to ICU admission. Persistent renal dysfunction was defined as a final serum creatinine value before hospital discharge (censored at 30 days after enrollment) that was  $\geq 200\%$  of the baseline creatinine value.

And will be evaluated at 60 and 90 days.

**Secondary objectives:** all the following will be at hospital discharge and 28 days after hospital discharge between the intervention group (iron replacement) compared to the control group (placebo).

- ferritin value, (pg/dL)
- transferrin saturation (%)
- Hemoglobin (g/dL)
- serum creatinine (mg/dL)
- start of renal support therapy (any type of renal support such as: intermittent hemodialysis, peritoneal dialysis or continuous therapies)
- recovery of renal function, considered as a decrease in serum creatinine and approaching  $<0.3\text{mg/dL}$  of basal creatinine
- death

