## 2. DESIGN OF THE STUDY

Randomized placebo-controlled clinical trial, randomization method in blocks of 5 by frequency of occurrence. In patients with acute kidney injury, they will be randomized to receive the administration of intravenous iron dextran in a single exhibition according to the Mg provided by the Virizzi formula compared to placebo.

The sample size determined 55 patients per group, with a standard deviation of 1.5.

$$n = [(Z_{\alpha/2} + Z_{\beta})^2 \times \{2(\sigma)^2\}] / (\mu_1 - \mu_2)^2$$
$$n = [(1.96 + 0.84)^2 \times \{2(1.5)^2\}] / (10.8 - 10)^2$$
$$n = 55,125$$

n = sample size required in each group  $\mu_1 - \mu_2 =$   
clinically significant difference = 0.8 or = standard  
deviation = 1.5

$Z_{\alpha/2}$ : 1.96

$Z_{\beta}$ : 0.84

Version 2.0, 29 June 2023

Effect of intravenous iron repletion on renal function in patients with iron deficiency and acute kidney injury, clinical trial. June 2023, HCG/CEI-1232/22

[name] [contact], [name] GUADALAJARA, JAL

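### The MAKE30 components run from different time origins, two of them from ICU admission, in a trial with no visible ICU entry requirement

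*Protocol*

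**What the plan says.** Protocol section 2.5 (Primary objective) defines MAKE30 as any of three components, each with its own time frame:

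- **Death:** "death from any cause prior to hospital discharge censored at 30 days after ICU admission".
- **New RRT:** "receipt of any modality of RRT between ICU admission and the first of (1) hospital discharge or (2) 30 days", and only "in a patient not known to have received RRT prior to ICU admission". The origin of the 30 days is not stated.
- **Persistent renal dysfunction:** based on the "final serum creatinine value before hospital discharge (censored at 30 days after enrollment"), compared with baseline creatinine.

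The definition then adds "And will be evaluated at 60 and 90 days", without an origin.

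The section Design of the study describes the randomised population without mentioning the ICU: "In patients with acute kidney injury, they will be randomized to receive the administration of intravenous iron dextran". Section 4.1 admits hospitalised patients with AKI by KDIGO creatinine criteria, within limits on age, baseline creatinine and iron status. Outside the endpoint definition, the ICU appears only in the background of section 2.4 (for example "About 50% of ICU patients with AKI die (4-12") and in reference titles.

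The secondary objectives separately list death and "start of renal support therapy (any type of renal support such as: intermittent hemodialysis, peritoneal dialysis or continuous therapies"), at discharge and 28 days later.

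**The concern.** ICU admission is a sound origin only if every patient is admitted to the ICU and randomised at about that moment. The visible text requires neither. Where ICU admission and randomisation are apart, or ICU admission never happens, the definition does one of three things: it gives no answer, it counts events that precede treatment, or it leaves out events that follow treatment.

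At stake is the classification of the primary endpoint. For never-ICU patients, whoever adjudicates RRT must apply a rule that the protocol does not contain. Events fixed before randomisation add the same expected amount to both arms and shrink the observable difference. Ward RRT that goes uncounted is an outcome that treatment could have affected.

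**Working it through.** **1. The plan's own figure.** Design of the study: n = (1.96 + 0.84)² × 2 × 1.5² / 0.8² = 7.84 × 4.5 / 0.64 = 55.125, stated as 55 per group. It reproduces. It is a calculation for a difference in means (10.8 − 10), so it neither depends on the MAKE30 definition nor plans power for it.

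**2. The definition applied to each type of patient.**

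| Patient | Literal result |
|---|---|
| (a) Never in the ICU | RRT has no window start and no reference point for being new. Death keeps its discharge bound but loses its 30-day cap. |
| (b) Randomised after ICU admission, RRT begun in between | Meets the new-RRT definition, so is a primary event that treatment cannot affect. |
| (c) Randomised L days after ICU admission | Death is followed for 30 − L days after randomisation: 25 days at L = 5, 20 at L = 10. Creatinine keeps 30 days, assuming enrolment equals randomisation. The same holds for RRT only if its unstated 30-day origin is ICU admission. |
| (d) ICU entry after randomisation, RRT begun earlier on the ward | Not counted. If it continues in the ICU it is still not new, because it began before ICU admission. |

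**3. Dilution from (b).** Let s be the share with RRT between ICU admission and randomisation, and let qC and qT be the control and iron-arm risks in everyone else. The recorded risk in each arm is s + (1 − s)q, so the recorded difference is (1 − s)(qC − qT). It is 0%, 5%, 10% or 20% smaller at s = 0, 0.05, 0.10 or 0.20, whatever the base rate.

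The protocol gives no MAKE30 rate and no s, so the following rates are assumed. Power is for two proportions with n = 55 per arm and two-sided alpha 0.05: Φ[(d − 1.96·SE0)/SE1], where d is the recorded difference, SE0 the pooled and SE1 the unpooled standard error.

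| qC vs qT | s = 0 | s = 0.10 | s = 0.20 |
|---|---|---|---|
| 0.30 vs 0.20 | 0.225 | 0.169 (0.37 vs 0.28) | 0.134 (0.44 vs 0.36) |
| 0.40 vs 0.20 | 0.632 | 0.498 (0.46 vs 0.28) | 0.392 (0.52 vs 0.36) |
| 0.50 vs 0.30 | 0.573 | 0.473 (0.55 vs 0.37) | 0.388 (0.60 vs 0.44) |

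One cell in full, 0.46 vs 0.28: d = 0.18; SE0 = √(0.37 × 0.63 × 2/55) = 0.0921; SE1 = √((0.46 × 0.54 + 0.28 × 0.72)/55) = 0.0905; (0.18 − 0.1805)/0.0905 ≈ −0.005; power 0.498.

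**4. What the fix could recover**, at 0.40 vs 0.20. Patients on RRT at randomisation are no longer automatic events. If they carry k times the countable risk of the others, each arm's risk is s·k·q + (1 − s)q. Expected events are 55 × (sum of the two risks).

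| | s = 0.10 | s = 0.20 |
|---|---|---|
| Current text | 0.498; 40.7 events | 0.392; 48.4 events |
| k = 0.5 | 0.600; 31.4 events | 0.567; 29.7 events |
| k = 2 | 0.694; 36.3 events | 0.753; 39.6 events |
| No treatment effect in these patients, risk 0.60 in both arms | 0.519 (0.42 vs 0.24) | 0.415 (0.44 vs 0.28) |

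The k = 2 row is an outer bound. It gives patients already on RRT risks of 80% vs 40%, a 40-point effect, which is why it exceeds the undiluted 0.632.

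**The case against.** The strongest reply is that the decisive text may simply not be visible. The heading of section 4.1 announces exclusion criteria but none can be read, and some pages were removed. If prior RRT is an exclusion, s is zero, case (b) disappears and every power figure above with it. If ICU admission is an entry criterion, (a) and (d) disappear. The introduction (section 2.2) does frame the rationale around critically ill patients. This stands as a condition on those cases. It does not remove the inconsistency, because the differing caps for death and creatinine lie within the endpoint definition itself. A rationale about critical illness is also not an entry criterion, and section 4.1 says hospitalised patients.

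Second, the size is hypothetical: no MAKE30 rate, ICU share or s is documented, and the power losses are measured from assumed baselines. That is correct. At 30% vs 20% power is low before any dilution.

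Third, (c) and (d) may concern few patients, and RRT start and death are also secondary outcomes. Both are true, but secondary outcomes do not repair the primary one.

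**Conclusion.** The concern holds and must be fixed. On the visible text, the RRT component of the primary endpoint cannot be determined for a class of eligible patients, and its components do not share an origin with each other or with randomisation. That conclusion is firm, needs no assumed rate, and is what the severity rests on.

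That pre-randomisation RRT counts as an event is conditional on no unseen exclusion. Its expected effect is loss of power, not bias under the null. The factor 1 − s is exact under the stated set-up, but s is unknown and may be zero. The number of ward-RRT events lost under (d) cannot be estimated from the documents.

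**What to change.** Use randomisation as the origin for all three components and for the 60- and 90-day evaluations. Keep the existing cut-off of hospital discharge or 30 days, whichever comes first. Define new RRT as first RRT after randomisation in a patient with no RRT before randomisation.

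State how patients already on RRT at randomisation are classified. Dialysis lowers serum creatinine, so the creatinine criterion alone could record a dialysis-dependent patient as event-free. One workable option is to count such a patient as having persistent renal dysfunction if still on RRT at the cut-off. This adds a criterion to the current definition, and the main correction does not depend on it.

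**Cost.** The primary endpoint definition would change within the planned study period (August 2022 to December 2023; this version is dated 29 June 2023), so the change should be dated and made before allocation is unblinded. It needs the randomisation date, the date of first RRT and, for patients on RRT at randomisation, RRT status at the cut-off. The protocol does not say whether these are recorded. The power gain is uncertain: from a few points, if treatment does nothing for patients already on RRT, to the larger figures in the working. The total event count may rise or fall, because counting ward RRT and shifting the windows add events that the documents do not allow to be estimated.

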### 4.1 INCLUSION AND EXCLUSION CRITERIA

#### criteria of **inclusion**:

Hospitalized patients with ARD, will be defined as the diagnosis using the KDIGO criteria of serum creatinine (Cr); Patients with AKI  $> 18$  and  $< 85$  years, baseline creatinine  $< 2$  mg/dL and with written informed consent will be included.

Iron deficiency according to the criteria of the 2: serum iron  $< 13$  ng/dL, transferrin saturation  $< 20\%$ .

Version 2.0, 29 June 2023

Effect of intravenous iron repletion on renal function in patients with iron deficiency and acute kidney injury, clinical trial. June 2023, HCG/CEI-1232/22

[name] [contact], [name] GUADALAJARA, JAL

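### A survivor dialysed before ICU admission and still on dialysis can be scored free of MAKE30, because continuing dialysis is not part of the primary endpoint

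*Protocol*

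**What the plan says.** Section 2.5 (Primary objective) makes the primary endpoint the proportion of patients with at least one of three events: "in-hospital mortality; receipt of new RRT; or persistent renal dysfunction".

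- **New RRT.** "Receipt of new RRT was defined as receipt of any modality of RRT between ICU admission and the first of" hospital discharge or "30 days in a patient not known to have received RRT prior to ICU admission". Anyone known to have been dialysed before ICU admission cannot meet this component.
- **Persistent dysfunction.** "Persistent renal dysfunction was defined as a final serum creatinine value before hospital discharge", censored at 30 days after enrolment, that is at least 200% of baseline. Whether the patient is on dialysis when the sample is taken plays no part.
- **Later time points.** The section adds "And will be evaluated at 60 and 90 days" and leaves the component definitions unchanged.

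Section 4.1 admits hospitalised "Patients with AKI" within an age range, with baseline creatinine below 2 mg/dL, iron deficiency and consent. Its title announces exclusion criteria, but only inclusion criteria follow. Nothing there or elsewhere in the protocol requires that a patient be free of RRT at entry.

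**The concern.** Not counting earlier RRT as new is reasonable in itself. The difficulty is that no other component then picks up the patient who stays on dialysis. For that patient, unless death occurs, the primary outcome rests on a creatinine value that depends partly on dialysis clearance and on when the sample was drawn, and not only on kidney recovery.

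Dialysis dependence is among the worst non-fatal outcomes a kidney trial can record. A rule that can code it as absence of a major adverse kidney event weakens what the primary result means, even if few patients are affected.

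**Working it through.** **The plan's own figure.** The sample size in the design section reproduces: (1.96 + 0.84)² × 2 × 1.5² / 0.8² = 55.125, printed as 55 per group. It rests on a difference in means of 0.8, not on MAKE30, so it gives no event rate for this check.

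**Scoring one patient by the stated rules.** Take a patient with AKI and a baseline creatinine below 2 mg/dL, whose acute dialysis starts before ICU admission and who is alive and still on dialysis at the final assessment.

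1. Eligible under section 4.1, if the other criteria are met: yes, since RRT is not mentioned.
2. Death: no.
3. New RRT: no, closed by definition.
4. Persistent dysfunction: only if the final creatinine is at least 2 × baseline. The threshold is 2.0 mg/dL for a baseline of 1.0, 3.0 for 1.5 and 3.8 for 1.9.
5. If the value on dialysis is below that threshold, all three components are negative and the patient is event-free.

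Evaluation at 60 and 90 days uses the same components, so it does not recover the patient.

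**Size.** The protocol gives neither a MAKE30 rate nor the share with prior RRT. The inputs below are assumptions:

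- true event rates of 50% (placebo) and 25% (iron), 55 per arm;
- a share q = 5% to 10% with RRT before ICU admission, equal in both arms and with the same event rates as other patients;
- half of the events in that group missed.

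The observed rate is the true rate × (1 − 0.5q). Power is by exact binomial enumeration of the two-sided Pearson chi-square test at 0.05.

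| q | Observed rates | Difference (points) | Power |
|---|---|---|---|
| 0 | 50.0% v 25.0% | 25.0 | 78.9% |
| 5% | 48.75% v 24.375% | 24.4 | 77.4% |
| 10% | 47.5% v 23.75% | 23.75 | 75.8% |

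Expected missed events are 55 × 0.05 × 0.5 × (0.50 + 0.25) = 1.0 at q = 5%, and 2.1 at q = 10%, in 110 patients.

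The power loss depends on the assumption that events are missed in proportion to the event rate. If both arms instead lose the same 2.5 percentage points, the difference stays at 25 points. By the normal approximation, power then moves from 78.1% to 79.3%, so it does not fall. Power is therefore not the main argument.

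**The case against.** The strongest case against is that the affected group is narrow.

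- The bar is RRT before ICU admission. RRT first given in the ICU, even before enrolment, still scores as an event.
- A baseline creatinine below 2 mg/dL would keep out most chronic dialysis patients, leaving mainly acute dialysis begun before ICU admission.
- Deaths always count. Section 2.4 puts mortality at about 50% for ICU patients with AKI, so the pool of dialysis-dependent survivors is limited.
- A survivor on dialysis with creatinine at or above twice baseline is also counted already.

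All of this stands, and it limits the size of the problem.

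It can also be said that scoring a creatinine taken on dialysis is a derivation detail for an analysis plan that is not shown. That is weaker. The protocol itself fixes the component as creatinine alone, and adding dialysis status would change the stated endpoint.

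Three stronger readings are tempting and are not supported:

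- **That one or two such patients could reverse the trial's conclusion.** Such examples need a result already close to 0.05 and missed events falling wholly or mainly in the placebo arm. The protocol gives no MAKE30 rate from which to build one.
- **That the secondary outcomes treat the same patient inconsistently.** The secondary outcome counts the start of renal support. A patient continuously on dialysis since before entry does not start it, so this outcome does not capture continuing dialysis either.
- **That a correction would rescore only patients with prior RRT.** Section 4.1 does not require ICU care, and the new-RRT window opens at ICU admission. Ward patients never admitted to ICU are not clearly covered by that component.

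**Conclusion.** The point holds as an endpoint-definition gap. Read together, sections 2.5 and 4.1 allow a survivor whose dialysis began before ICU admission, and who is still dialysed at the final assessment, to be scored event-free when creatinine is below twice baseline. This outcome is possible but not certain for each such patient.

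How many patients are affected cannot be derived from the protocol. The number is probably small: about 1 to 2 of 110 under the assumptions above, with power falling by about 1.5 to 3 percentage points. Those figures rest on assumed event rates, an assumed prior-RRT share and an assumed half of events missed. They would change with any of these, and the power loss disappears if both arms lose the same number of events. The case for correcting the definition is validity: the primary endpoint should not be able to record ongoing dialysis as a good kidney outcome.

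**What to change.** In section 2.5, extend the third component to read: *final serum creatinine ≥ 200% of baseline, or still receiving any RRT at the final assessment, whenever RRT began*. Leave the new-RRT component restricted as it is. Record RRT status (yes/no) at randomisation and at the final assessment. Report MAKE30 with and without patients on RRT at randomisation as a sensitivity analysis.

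The addition will also score as events those patients never admitted to ICU who are on RRT at the final assessment. The protocol should say so openly, since the present ICU-based window does not clearly cover them.

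The cost is one sentence and a yes/no item at two time points. Section 2.5 already has nephrology staff assessing patients for adverse events every 24 hours in hospital. No extra patients or procedures are needed. The downside is a slightly higher event rate and a departure from the present component wording.

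### All secondary outcomes are timed from hospital discharge rather than from randomisation, so laboratory values are read at uncontrolled times and events over unequal windows, and the comparison can be biased if iron changes length of stay or survival

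*Protocol*

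**What the plan says.** Protocol section 2.5 lists seven secondary outcomes: ferritin, transferrin saturation, haemoglobin, serum creatinine, start of renal support, recovery of renal function, and death. One timing rule covers them all: "all the following will be at hospital discharge and 28 days after hospital discharge between the intervention group" and the control group. None has a fixed day from randomisation, enrolment or infusion. Recovery rests on a laboratory value: "recovery of renal function, considered as a decrease in serum creatinine and approaching" the baseline level within a stated margin.

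The primary endpoint in the same section is limited to 30 days, and its death component is bounded by discharge: "In hospital mortality was defined as death from any cause prior to hospital discharge censored at 30 days after ICU admission". A sentence after the primary endpoint adds "And will be evaluated at 60 and 90 days"; it names no visit and no blood draw.

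Section 2.6 expects iron to improve renal function, iron deficiency and anaemia. The design section describes one administration of iron and daily blood counts and creatinine. (It also says that drugs were given every day. Those two statements must be reconciled, but this point does not depend on which applies.)

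**The concern.** A secondary comparison keeps the protection of randomisation when both arms are read at the same time from randomisation and every randomised patient is accounted for. A discharge anchor weakens both conditions.

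- **Time.** When a patient goes home depends partly on renal recovery, which the trial hopes to change. Haemoglobin, iron indices and creatinine all move with time since the infusion or the renal insult. If one arm goes home earlier, it is read earlier on those curves.
- **Who is read.** A patient who dies in hospital never reaches 28 days after discharge, and the protocol gives no rule for that patient. If iron changes survival, the patients read in the two arms are differently selected.

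At stake is the interpretation of the haemoglobin, iron and renal-function results. A statistical analysis plan could choose an analysis set or a missing-data method, but it could not recover blood samples at a common day after discharge if none were scheduled.

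**Working it through.** **Inputs from the protocol.** The design section gives a difference of 0.8 (10.8 against 10), an SD of 1.5, and z values of 1.96 and 0.84. It does not name the variable. The scale fits haemoglobin in g/dL, and that is an assumption here.

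**The plan's own figure.** n = (1.96 + 0.84)² × 2 × 1.5² / 0.8² = 7.84 × 4.5 / 0.64 = 55.125 per group. The stated 55 reproduces. It serves below only as the source of the 0.8 yardstick and the SD.

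**Step 1: what the timing rule does to each outcome.**

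| Outcome | Reading at discharge | Reading 28 days after discharge |
|---|---|---|
| Ferritin, transferrin saturation, haemoglobin, creatinine, recovery (5 of 7) | Time since infusion differs by patient | The same, and only in patients discharged alive |
| Death, start of renal support (2 of 7) | Countable in all; window equals the stay | Window equals stay + 28 days; undefined after an in-hospital death |

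With assumed discharges 4 and 25 days after infusion, the event windows are 4 + 28 = 32 days and 25 + 28 = 53 days.

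**Step 2: survivor selection (assumed mortality and correlation).** Suppose iron has no effect on any patient's haemoglobin, survival depends on a normal frailty score, and that score has correlation r with haemoglobin. With mortality m, mean haemoglobin in survivors exceeds the overall mean by SD × r × φ(z_m)/(1 − m).

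- Mortality 30% placebo, 20% iron, r = 0.5: 1.5 × 0.5 × (0.497 − 0.350) = 0.11 g/dL against iron.
- Mortality 50% and 40%: 0.07 (r = 0.3) to 0.12 (r = 0.5) against iron.
- Mortality 50% and 30%: 0.14 (r = 0.3) to 0.23 (r = 0.5) against iron.
- Equal mortality: 0.

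**Step 3: difference in stay (assumed slope and stay).** Shift = slope per week × difference in days / 7.

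- Smallest case: 0.1 × 2/7 = 0.03 g/dL.
- Middle case: 0.25 × 4/7 = 0.14 g/dL.
- Largest case: 0.5 × 7/7 = 0.50 g/dL.

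If haemoglobin is rising and iron shortens stay, the shift goes against iron. With equal mean stay it is 0. Against the yardstick of 0.8, step 3 runs from about 4% (0.029/0.8) to 63% (0.50/0.8), and the first case in step 2 is 14% (0.11/0.8).

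**The case against.** The best defence is that the bias is conditional and possibly small. Section 2.6 says nothing about length of stay, and no expected mortality is given. The background statement "About 50% of ICU patients with AKI die" concerns ICU patients, while section 4.1 admits hospitalised patients with no ICU requirement. Daily in-hospital tests give fixed-day inpatient values for blood count and creatinine. The handling of deaths may be in an analysis plan that is not shown. All of this stands. It limits the size that can be claimed, but leaves the discharge anchor in place and supplies no common-time reading after discharge.

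Four stronger readings are tempting and are not supported.

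- **All seven outcomes are survivor-only.** Death and start of renal support can be counted in everyone randomised.
- **A mortality benefit would be reversed.** Assume in-hospital death of 30% on placebo and 20% on iron. Assume also that half of the 10% saved, and 5% of the others discharged, die afterwards. Among those discharged, later death is 5.0% on placebo against (0.70 × 0.05 + 0.10 × 0.50)/0.80 = 10.6% on iron. Section 2.5 sets no such denominator. Counted in all randomised patients, the same figures give 33.5% against 28.5%, correctly in favour of iron.
- **Early reading in itself biases the arms.** If a 0.8 gain built linearly over 28 days, day 5 would show 0.8 × 5/28 = 0.14 and day 14 would show 0.40. That is a smaller visible effect, not a bias between arms. Under the same model, every reading 28 days after discharge comes at least 28 days after an in-hospital infusion and shows the full gain.
- **Day-30 and day-90 visits already exist.** The 30-day components stop at discharge, and the 60- and 90-day sentence follows only the primary endpoint. The schedule of activities is an attachment that is not shown.

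**Conclusion.** The discharge anchor is a real and avoidable weakness of the secondary outcomes. Patients will be read at different times since infusion. Five of the seven outcomes will lack a later reading for patients who die in hospital. The other two have unequal follow-up windows that are undefined at the later point after an in-hospital death.

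That the arms differ systematically is possible but not established; it needs an effect of iron on stay or survival. The size is unknown. Under the assumed inputs it is about 0.1 g/dL from survivor selection with a 10-point mortality difference and correlation 0.5, and 0.03 to 0.50 g/dL from differing stay. The documents do not support a claim that a true benefit would be hidden or reversed. The point concerns secondary outcomes, and the change is worthwhile because it is cheap.

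**What to change.** In section 2.5:

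1. Replace the assessment 28 days after discharge with one fixed day from randomisation, for example day 30, in hospital or out, by re-timing the post-discharge assessment already planned.
2. Count death and start of renal support cumulatively from randomisation to that day in all randomised patients.
3. Count patients who die before that day as not recovered.
4. Keep discharge values as descriptive.

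A fixed day removes the timing problem. It does not remove selection by death from the four laboratory values, so those should be labelled as values in survivors and shown beside mortality.

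**Cost.** The change is to wording and to the date of one assessment. That assessment falls on a calendar date, so follow-up after discharge is shorter for patients with long stays. Patients still in hospital on that day need their iron indices drawn then instead of later. A day-90 iron panel should not be described as already planned; adding one would be a new procedure.
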